#### 5.4.2 Key secondary analysis

The three secondary endpoints are analyzed in identical fashion to the primary analysis, defined in section 5.4.1.

### 5.5 Rule of exclusion criteria of analysis sets

#### Table 5-1 Protocol deviations that cause subjects to be excluded

The table below shows the selected PDs leading to exclusion of the subject from analysis:

Check condition	Protocol Deviation ID (DVSPID)	Description used to Report PDs to HA/IRBs (DVTERM)	PD category - text description (DVDECOD)	Exclusion form analysis
No informed consent signature.	INCL01	No informed consent signature.	SELECTION CRITERIA NOT MET	Exclude from all analysis
Patient randomized but no study medication taken.	TRT04	Patient randomized (who have completed Randomization Visit) but no study medication taken.	TREATMENT DEVIATION	Exclude from SAF analysis
Patient was randomized in error but did NOT receive any study medication.	*OTH10	Patient was randomized in error but did NOT receive any study medication.	OTHER	Exclude from FAS and SAF analysis
Not Hospitalized due to acute decompensated HF episode (ADHF primary diagnosis), including signs and symptoms evaluation at admission.	*INCL03	Not Hospitalized due to acute decompensated HF episode (ADHF primary diagnosis), including signs and symptoms evaluation at admission.	SELECTION CRITERIA NOT MET	Exclude from FAS and SAF analysis
Patient not starting treatment within protocol specified windows.	OTH13	Patient not starting treatment within protocol specified windows	OTHER	Exclude from FAS analysis

\*Subjects with PDs INCL03 and/or OTH10 are considered to have been inadvertently randomized into the study.

**Table 5-2 Subject classification**

Analysis Set	PD ID that cause subjects to be excluded	Non-PD criteria that cause subjects to be excluded
RAN	INCL01	Patients that did not sign ICF
FAS	INCL01, OTH10, INCL03, OTH13	
Patients that did not sign ICF
 
Patient was randomized in error but did NOT receive any study medication.
 
Patients not hospitalized for acute decompensated heart failure as primary diagnosis (not the same population)
 
Patient not starting treatment within protocol specified windows.

SAF	INCL01, TRT04, OTH10, INCL03	
Patients that did not sign ICF
 
Patient randomized but no study medication taken
 
Patient was randomized in error but did NOT receive any study medication.
 
Patients not hospitalized for acute decompensated heart failure as primary diagnosis (not the same population)

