9.1 Analysis sets

The following populations will be used for the statistical analyses:

Randomized Population (RAN) will consist of all patients randomized.

The full analysis set (FAS) will consist of all randomized patients with the exception of those patients who have not received study drug, but have been inadvertently randomized into the study. Following the intent-to-treat principle, patients will be analyzed according to the treatment to which they were assigned at randomization.

The Safety Population (SAF) will consist of all randomized patients who received at least one dose of study drug. Patients will be analyzed according to treatment actually received. The safety population will be used for the analyses of safety variables.

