## 2.2 Analysis sets

The following populations will be used for the statistical analyses:

- Screened set (SCR) – All patients who signed the informed consent. The SCR includes only unique screened patients.
- Randomized Population (RAN) will consist of all patients randomized.
- The full analysis set (FAS) will consist of all randomized patients with the exception of those patients who have inadvertently been randomized into the study. In addition, patients not starting treatment within protocol specified windows will be excluded from FAS. Following the intent-to-treat principle, patients will be analyzed according to the treatment to which they were assigned at randomization.
- The Safety Population (SAF) will consist of all randomized patients who received at least one dose of study drug with the exception of those patients who have inadvertently been randomized into the study. Patients will be analyzed according to treatment actually received. The safety population will be used for the analyses of safety variables.

The protocol deviation codes leading to exclusion from the analysis sets defined above are presented in the section 4.5 Rule of exclusion criteria of analysis sets.

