### 4 Change to protocol specified analyses

- The definition of the full analysis set (FAS) was updated to exclude patients who have inadvertently been randomized, regardless the study medication intake.
- The definition of the safety analysis set (SAF) was updated to exclude patients who have inadvertently been randomized, regardless the study medication intake.
- Creatinine kinase parameter is not analyzed as the data have not been collected.

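### The SAP's Safety Population would leave out any dosed patient coded INCL03, and no planned adverse-event summary would include that patient

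*SAP*

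**What the plan says.** - Protocol 9.1: the safety set "will consist of all randomized patients who received at least one dose of study drug", with no exception for eligibility. The protocol's FAS also keeps dosed patients, because it drops the inadvertently randomised only when they took no drug.
- SAP 2.2 adds an exception to that definition: "all randomized patients who received at least one dose of study drug with the exception of those patients who have inadvertently been randomized into" [this trial].
- SAP Table 5-1, footnote: "Subjects with PDs INCL03 and/or OTH10 are considered to have been inadvertently randomized into the study".
- SAP section 4 makes clear that dosing does not matter: "The definition of the safety analysis set (SAF) was updated to exclude patients who have inadvertently been randomized, regardless the study medication intake".
- SAP Table 5-2: the codes that remove a patient from SAF are "INCL01, TRT04, OTH10, INCL03"; those for FAS are "INCL01, OTH10, INCL03, OTH13". The only reason offered for INCL03 is a remark in the same table: "Patients not hospitalized for acute decompensated heart failure as primary diagnosis (not the same population".
- Use of the sets: SAF serves the primary endpoint (SAP 2.5.1) and the safety variables (SAP 2.2). FAS serves a supportive primary analysis (SAP 2.5.4) and the analysis of adverse events since randomisation (SAP 2.8.1). RAN serves the baseline tables (SAP 2.3) and, with SCR, disposition (SAP 2.3.1).

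**The concern.** A safety set is meant to hold everyone who was exposed. Finding later that a patient did not meet an entry criterion does not undo the exposure. A patient admitted for another primary diagnosis, then randomised and dosed, would contribute no adverse event, death, laboratory abnormality or drug discontinuation to any SAF table. That matters in a trial whose stated aim (Protocol 3.1) is to inform on the safety and tolerability of starting LCZ696 around discharge.

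The same set carries the primary risk ratio, so the exclusion also enters the main result, and no planned analysis lets a reader see what it did. The trial is open-label, and the SAP does not state that INCL03 is coded blind to arm.

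**Working it through.** **1. Which codes can remove a dosed patient?** (SAP Tables 5-1 and 5-2)

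| Code | Concerns | Can the patient have been dosed? | Out of SAF | Out of FAS |
|---|---|---|---|---|
| INCL01 | no consent signature | possibly | yes | yes |
| TRT04 | randomised, took no drug | no | yes | no |
| OTH10 | randomised in error, took no drug | no | yes | yes |
| INCL03 | index admission not primarily for ADHF | yes | yes | yes |
| OTH13 | did not start within the allowed window | yes | no | yes |

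The exception for inadvertent randomisation consists of INCL03 and OTH10. OTH10 patients took no drug, so they could never have been in a set that requires a dose. The added exception therefore changes SAF only through INCL03. INCL01 is not contested here.

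**2. Which planned outputs would contain a dosed INCL03 patient?**

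- SAF safety tables: no.
- Adverse events since randomisation, on FAS: no.
- Primary endpoint on SAF, on evaluable SAF patients, and on FAS: no in all three.
- Secondary endpoints, analysed in the same way as the primary (SAP 2.8), including discontinuation for adverse events: no.
- Baseline and disposition on RAN: yes.

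**3. Reproducing the plan's own figure.** Inputs: about 1000 patients (SAP section 3), 1:1 allocation (SAP 1.1), 80% success in both arms. The 95% CI is exp(ln RR ± 1.96 × SE), with SE = √[(1−p₁)/(n₁p₁) + (1−p₀)/(n₀p₀)].

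SE = √[0.20/(500×0.80) + 0.20/(500×0.80)] = √0.001 = 0.0316. The CI is exp(±0.0620) = 0.940 to 1.064. The plan prints 0.94 to 1.06, so the figure is reproduced. It does not depend on the INCL03 rule.

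**4. How far could the exclusion move the risk ratio?** The documents give no count of dosed INCL03 patients, so the numbers omitted (k) are assumptions. The calculation ignores the three strata.

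*Balanced omission, 80% in both arms:* 25 omitted per arm gives 0.938 to 1.066, and 50 per arm gives 0.937 to 1.068. Precision hardly changes.

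*One-sided extreme:* the full data are 400/500 in each arm, and k patients are omitted from Pre-discharge only. If all k are failures, RR = [400/(500−k)]/0.80. If all are successes, RR = [(400−k)/(500−k)]/0.80.

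| k | all failures: RR (95% CI) | all successes: RR (95% CI) |
|---|---|---|
| 5 | 1.010 (0.950, 1.074) | 0.997 (0.937, 1.062) |
| 10 | 1.020 (0.960, 1.084) | 0.995 (0.934, 1.059) |
| 20 | 1.042 (0.982, 1.105) | 0.990 (0.929, 1.054) |

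For example, with k = 10 failures, 400/490 = 0.8163, and 0.8163/0.80 = 1.020.

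**The case against.** The case for the SAP has several parts.

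- **The change is disclosed.** SAP section 4 lists it. That is true, but disclosure does not make the set complete.
- **INCL03 is unlike other entry criteria.** Admission for ADHF defines the population, so treating it differently from a breached potassium or blood pressure limit can be justified. This stands for the primary endpoint, where restricting on a fact fixed before randomisation is defensible. It does not carry over to safety tables, where exposure is what counts.
- **The information is not lost altogether.** Study discontinuations with reasons are tabulated on RAN, serious events are still reported individually to the sponsor (Protocol 7.3.2), and significant deviations go into the study report (Protocol section 11). This is correct, so the loss concerns the SAF and FAS summaries. None of these outputs replaces an adverse-event table.
- **The primary analysis only estimates.** SAP 5.4.1 plans no test, and the shifts shown above are small. This also stands.

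A reader might infer that INCL03 is an unblinded judgement made after randomisation. The documents do not support that. The code rests on the diagnosis and the signs and symptoms at admission, monitors verify the entry criteria (Protocol 8.1), and sponsor staff are to stay blinded as far as possible (Protocol 3.5). Protocol 5.4 concedes that accidental unblinding can occur, and the documents do not say who assigns the code. What can be said is that blind coding is not specified.

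**Conclusion.** The point holds as a matter of definition. Under the SAP as written, any dosed patient coded INCL03 would be missing from the safety tables and from every planned adverse-event summary, contrary to Protocol 9.1. The safety tables are the main ground. The effect on the primary result is secondary and probably small: RR 1.02 if 10 failures were omitted from Pre-discharge only, and almost no change in precision if omissions are balanced. Those figures rest on assumed counts and on an unstratified calculation.

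Two stronger readings should be resisted.

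- A reader might take it as fact that exposed patients have been omitted. The documents give no count of dosed INCL03 patients, and it may be zero.
- A reader might size the loss by applying the angioedema rate of 19/4187 in Protocol 3.6 to 1000 patients, which gives about 4.5 events, so that one lost case would be about a fifth. That rate comes from a trial with a median follow-up of 27 months (about 117 weeks), whereas this study lasts 26 weeks. At constant hazard the figure is 4.5 × 26/117, or about 1. The earlier trial also excluded current acute decompensation, and risk need not be constant over time. The documents therefore support no expected number of lost events.

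**What to change.** 1. Define SAF as all randomised, consented patients who received at least one dose. Keep the INCL01 exclusion; a literal return to the protocol sentence would drop it.
2. Remove INCL03 from the SAF entries in Tables 5-1 and 5-2, and align SAP 2.2 and section 4.
3. Report the number of dosed INCL03 patients by arm.
4. If an ADHF-only result is wanted for the primary endpoint, run it on a separately named set and show the primary endpoint both with and without these patients.
5. State whether INCL03 is coded blind to arm.

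The cost is SAP wording and one flag in the analysis-set derivation. No new data are needed. If the count of dosed INCL03 patients is zero, the SAF outputs do not change.
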